#### 1.6.5. Communication of group allocation with the nursing staff and parent(s):

The responsibility for communicating group allocation lies with the study coordinator. Following the completion of the randomization process, parents and nursing staff will be informed of the group allocation, as the study is open-label, and this information aligns with the study design. During this discussion, parents will receive a clear explanation of their infants' group assignment, including its implications and details regarding the associated supplementation. It will also emphasize the voluntary nature of participation and the option for parents to withdraw from the study at any point.

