#### 1.6.2 Exclusion criteria:

Enrollment in any other clinical study affecting nutritional management during the feeding intervention; anticipated change in primary caregiver (person providing the feed) prior to 4 months; refusal to consent to donor milk; supplementation with formula prior to enrollment; any physical condition that may impact growth (ex: skeletal dysplasia).

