#### 1.8 Sample size estimation and power calculations

According to the systematic scoping review of McCune and Perrin published in January 2021, there are no data from RCTs comparing donor milk to formula for supplementation of late preterm or term newborns (13). The only available RCT is a pilot study that assessed the feasibility of using donor milk versus formula for a small group of 32 full-term and late preterm infants admitted to NICU; even though this study did assess certain aspects related to breastfeeding, such as feeding attempts and growth, the authors emphasized the need for larger-scale studies to validate the findings of this pilot study (15). The current exclusive breastfeeding rate in Toronto at 4 months of age is 28% (31). In one retrospective review following donor milk supplementation in late preterm and term newborns ( $\geq$ 35 weeks gestational age), the rate of exclusive breastfeeding rate to 56% would be clinically significant and plausible given the published data and was thus used for sample size calculation. With 80% power and an alpha level of 0.05, we require 47 infants in each of the two study arms. We anticipate, based on our prior work, a 15% loss to follow-up to 4 months of age (32); hence 56 infants will be recruited for each study arm or 112 infants in total.

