#### 1.9 Analyses

#### 1.9.1 The proposed type of analyses:

Analyses will be carried out using SAS Version 9.4. Descriptive statistics will be calculated for all variables of interest. Unadjusted and adjusted models will be run to compare primary, secondary and exploratory outcomes. The primary outcome of exclusive human milk feeding will be compared between groups using a linear regression model. Secondary and exploratory outcomes will be assessed using linear and logistic regression models based on the nature of the outcome measure. The models will be adjusted for risk condition (being born to a diabetic mother or SGA) and sex. The primary analysis for this intent-to-treat study will include all infants as randomized, regardless of feeding protocol compliance.

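### Eligibility screens out refusal of donor milk but not of formula, and withdrawal from the study is stressed as the open allocation is disclosed, so the primary contrast may be biased towards donor milk

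*Protocol*

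**What the plan says.** **Eligibility (Protocol 1.6.1, 1.6.2).** Parents must intend to feed parent milk. The exclusions include "refusal to consent to donor milk; supplementation with formula prior to enrollment". Others concern enrolment in another nutrition study, a change of caregiver and conditions affecting growth. Refusal of donor milk is the only exclusion that turns on the family's view of a supplement.

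**Consent and allocation (1.6.4).** Families consent antenatally and confirm their willingness to take part on admission. They are randomized 1:1 once a supplement is prescribed.

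**Disclosure (1.6.5).** The coordinator then tells parents and nurses the open-label allocation. Of that discussion the section says: "It will also emphasize the voluntary nature of participation and the option for parents to withdraw from the study at any point".

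**Analysis (1.9.1).** "The primary analysis for this intent-to-treat study will include all infants as randomized, regardless of feeding protocol compliance". The adjustment covariates named are risk condition and sex.

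**Outcome and size (1.7, 1.8).** Exclusive human milk feeding is parent-reported. The design assumes 28% against 56%, with 15% loss by 4 months given as one figure and not by arm.

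**The concern.** The two arms hear the same words at disclosure but have been screened differently. Families averse to donor milk have been removed; families averse to formula have not. Section 1.4 calls formula the current standard supplement, so for some families the attraction of joining may be the chance of donor milk. A family of that kind allocated to formula learns this in the conversation that stresses leaving the study. The option named there is leaving altogether, not declining the supplement while still answering the monthly questions.

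If such families leave, and would have been more likely than average to feed human milk exclusively at 4 months, the formula arm loses successes out of proportion. Keeping non-compliers in the analysis does not help, because the missing item is the outcome itself. The protocol expects parents to respond to which supplement they are given: section 1.6 sets out to study the effect of awareness, and section 1.7 expects the value placed on human milk to drive the effect. A preference-driven response is therefore plausible.

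**Working it through.** **1. The plan's own figure.** Inputs from 1.8: 28% and 56%, 80% power, alpha 0.05 (taken as two-sided). With pooled variance:

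n = [1.96·√(2·0.42·0.58) + 0.8416·√(0.28·0.72 + 0.56·0.44)]² / 0.28² = (1.368 + 0.563)² / 0.0784 ≈ 47.6, so 48. The arcsine formula gives 47.3.

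The stated 47 is reproduced to within one infant. Inflation: 47/0.85 = 55.3, so 56 per arm, as stated. The sample size is not in dispute.

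**2. Bias from selective withdrawal.** Suppose there is no true effect, with 28% in both arms. Expected successes per arm are 0.28 × 56 = 15.68. Let w formula families leave at disclosure with no outcome, and let q be the rate they would have had. Among those retained:

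observed formula rate = (15.68 − w·q) / (56 − w)

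Neither w nor q is in the documents; both are assumed. The donor arm is kept at 56 and 28%. Rejection is the exact binomial probability that an unpooled z test passes ±1.96.

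| w | q | Observed formula rate | False difference | Two-sided rejection |
|---|---|---|---|---|
| 8 | 28% (no selection) | 13.44/48 = 28.0% | 0 | 5.8% |
| 4 | 56% | 13.44/52 = 25.8% | 2.2 points | 6.2% |
| 8 | 40% | 12.48/48 = 26.0% | 2.0 points | 6.5% |
| 8 | 56% | 11.20/48 = 23.3% | 4.7 points | 9.8% |
| 8 | 75% | 9.68/48 = 20.2% | 7.8 points | 17.4% |
| 14 | 56% | 7.84/42 = 18.7% | 9.3 points | 22.0% |

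The 5.8% in the first row is the test's own small-sample excess over 5%, so the other rows should be read against it. The last row is extreme: 14 × 0.56 = 7.84 is half of the 15.68 expected successes.

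**3. Allowing for loss in the donor arm.** Let 15% of the donor arm be lost at random and 15% of the formula arm leave selectively. With a pooled normal approximation, rejection is 5.6% at q = 40%, 8.5% at q = 56% and 18.3% at q = 80%. The picture is the same.

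**4. Counting leavers as failures.** This does not remove the problem if withdrawal is confined to one arm. With w = 8 and no selection (q = 28%), the formula rate reads 13.44/56 = 24.0%, a false difference of 4 points.

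**The case against.** The strongest reply is that consent already covers both arms. A family unwilling to accept formula would have to agree twice, antenatally and on admission, to an even chance of it. The one-sided criterion has an innocent reading: donor milk is the non-standard product, so its refusal is the one that needs naming. Leaving also appears to gain the family little. Under 1.12.1 the donor milk on the unit is held in a fridge reserved for the trial, and no section describes another route to it. Reminding parents that they may withdraw is an ordinary safeguard, given to both arms.

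Much of this stands, and it makes large-scale withdrawal less likely. It does not close the gap. The reconfirmation in 1.6.4 concerns willingness to take part, not acceptance of either supplement, and a disappointed family may leave without gaining anything by it.

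Three stronger readings are tempting and are not supported:

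- **That refusing donor milk is the only exclusion.** Section 1.6.2 lists several; what is missing is the counterpart for formula.
- **That parents are never told they can stop the supplement and stay in follow-up.** Consent pages are not available for review, and section 1.7 does speak of an infant exiting the feeding intervention. The point is only that 1.6.5 does not make the distinction when it matters most.
- **That the 15% loss allowance shows eight formula families will leave for this reason.** It is an overall figure to 4 months, for any cause and in both arms.

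**Conclusion.** The point holds as a design weakness with a possible bias, not a demonstrated one. The one-sided criterion and the timing of the withdrawal message are in the text, and intention to treat cannot supply an outcome that was never collected. The direction, towards donor milk, depends on formula-arm leavers being more committed to human milk than stayers. The documents give no preference or withdrawal data by arm, so a reader should not infer that the effect will be inflated.

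Under the assumptions shown, the bias is zero without selection and about 2 to 5 points at moderate values, with false rejection of roughly 6% to 10%. It is large only at extreme values. Against the 28-point difference the trial is designed to detect, the moderate figures are small, but they are avoidable. This is a cheap improvement rather than a flaw that undermines the trial.

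**What to change.** 1. **Section 1.6.2:** make the criterion symmetric, excluding families unwilling to accept either of the two supplements.
2. **Section 1.6.4:** at the existing reconfirmation on admission, before the envelope is opened, ask whether the family would accept either allocation, and place the emphasis on voluntariness there.
3. **Section 1.6.5:** tell parents in both arms, in the same words, that they may stop the assigned supplement and remain in follow-up to 4 months. Keep full withdrawal as a separate and unchanged right.

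None of this alters how an infant is fed or when a supplement is prescribed. The cost is a short amendment to the protocol and consent script, and the loss of a few families who would accept only donor milk. No visits or staff are added. The change protects only families enrolled after it, since outcomes already lost cannot be recovered at analysis.

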### 1.7 The outcome measurements at follow up

All outcome measures post hospital discharge may be assessed in person or virtually according to the family's preference. Outcome measures at birth will be assessed during the initial hospitalization whereas outcomes at 1, 2, and 3 months will be assessed by digital survey (RedCap) or telephone call according to the parent(s)' preference with the option of the 4 month visit being by telephone, video call or in person according to the parent(s)' preference.

#### Infant Feeding Intentions:

At baseline, the Infant Feeding Intentions (IFI) scale (19) will be employed to quantitatively measure the intensity of mothers' intentions to commence breastfeeding and sustain it as the exclusive source of nourishment for their infants for the recommended duration of 6 months, as advocated by public health agencies. The IFI scale is a valid and simple tool comprised of five carefully constructed questions designed to capture the essence of these intentions accurately.

The initial two items of the scale focus specifically on assessing the strength of intention to initiate breastfeeding, offering valuable insights into the mother's commitment from the outset. Subsequently, the remaining items of the scale examine the intensity of intention to exclusively breastfeed at distinct milestones: 1 month, 3 months, and 6 months of age.

By utilizing the IFI scale, our study aims to obtain a precise and quantitative understanding of the degree of intention and dedication displayed by mothers towards initiating and maintaining breastfeeding. This comprehensive evaluation will provide valuable insights into the dynamics of infant feeding practices, enabling the development of effective strategies and interventions to support and encourage breastfeeding.

#### Exclusive human milk feeding and informal shared milk feeding:

As previously mentioned, parent report will be taken at 1, 2, 3, and 4 months. At each interaction, participants will be asked whether the infant is receiving any human milk (yes/ no) and about exclusive human milk feeding. Exclusive human milk feeding will be defined as the provision of only human milk with no additional fluids (including water) or solids except for vitamins/minerals and medicine (including rehydration solutions). Based on previous research, we will explore human milk feeding "at" each time-point (within the previous 2 weeks of the interaction) as well as "for" each time interval (e.g., from hospital discharge to 4 months) (20). We anticipate the intervention will increase both the duration and exclusivity of human milk feeding due to the value given to human milk provision in this study. In order to understand the potential impact of increased informal milk sharing in situations where donor milk is not available after hospital discharge, we will investigate the frequency of this practice. To gather this information, we will include questions in our monthly check-in questionnaire for parents. Specifically, we will ask parents to indicate the number of times per day their infant was fed expressed human milk using a bottle, supplemental nurser, or other methods. Additionally, we will inquire whether the milk used for these feedings was expressed by the parent themselves or by someone else or whether it was a non-human milk based formula. By collecting this data, we aim to gain insights into the prevalence of informal milk sharing and its potential implications for infant feeding practices.

# Length of hospital stay, percent weight loss and glucose concentrations during initial hospitalization:

Infant weight is routinely measured at birth and daily during the initial hospital stay at the recruiting site and therefore these values will be abstracted from the patient chart. Donor milk in preterm children has been linked to slower weight gain, thus an important secondary outcome will be to document any difference in percentage weight loss for infants supplemented with donor milk compared to formula while in hospital. When considering the measure of percentage weight loss, it is important to take into account the natural fluid loss that occurs in the early postnatal period. To ensure the measure is meaningful in relation to fluid loss, the aim of the study is to document any excessive and unanticipated weight loss beyond what would be expected in the normal course of fluid regulation. This measure will help determine if there are any notable variations or concerns related to fluid loss that may affect the infants' overall wellbeing and growth outcomes. In addition, to investigate the effect of donor milk/ formula on

improving hypoglycemia in infants, the glucose concentrations at discharge will be extracted from patient charts and compared between groups.

For infants in the donor milk group, if infant weight loss is >3% per day, the clinical team will be alerted. If this occurs on any two consecutive days, the infant will exit the feeding intervention. Similarly, if the infant's blood glucose remains <2.6 mmol/L for two consecutive checks, the infant will exit the feeding intervention.

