#### 1.2 Research Background

For this proposed research, human milk refers to the totality of parent milk and donor milk. Parent milk is a gender inclusive term used for planning future research whereas mother's milk is used where describing reports from the literature where gender is not further specified. Donor milk refers to pasteurized human donor milk from an accredited milk bank.

Newborns are typically fed via parent milk as the primary source of nutrition and the multitude of benefits of mother's milk are summarized in the 2016 Lancet breastfeeding series (1). According to the recent 2023 Lancet breastfeeding report (2), although breastfeeding has been proven to have health benefits for mothers and infants in both high-income and low-income settings, less than 50% of infants worldwide are being breastfeed in accordance with the World Health Organization's (WHO) recommendations. This is due to a variety of factors, including societal, political, and economic influences (3, 4).

When a supplement to parent milk is required in the newborn period, it is uncertain whether this should be formula or donor milk as the former is associated with a reduction in exclusive human milk feeding later in infancy while the latter caries elevated financial cost and inequitable distribution within Canada and globally (5, 6). The impact of using donor milk versus formula as a supplement during initial hospitalization on adherence to breastfeeding guidelines post-discharge is unknown. There are more than 350,000 (7) infants born annually in Canada of whom approximately 90% are admitted to well-baby units with many hospitals reporting a typical formula or donor milk supplementation rate of about 35-50%, particularly for high risk infants (6). The reasons for supplemental feeds include hypoglycemia, hyperbilirubinemia, weight loss, insufficient volume of parent's milk, surrogacy, parental preference or for unknown reasons.

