#### 1.3.2 Secondary research objectives:

To explore whether the provision of donor milk as a supplement to parent's milk affects any, or exclusive, human milk feeding rates at 1, 2, and 3 months of age, breast feeding self-efficacy scores at 1, 2, 3 and 4 months, infant health and growth at hospital discharge and at 1, 2, 3, and 4 months, and percent weight loss, glucose levels, length of hospital stay at hospital discharge.

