#### 1.6.3 Guidelines for feeding during the intervention phase

The randomization occur once trial registration occurs. The intervention will continue throughout the hospitalization at any time that a supplementation is recommended by the clinical team, and is expected to last from 0 to 72 hours post-birth.

All donor milk will be aliquoted into individualized containers in the Rogers Hixon Ontario Human Milk Bank which is located in Sinai Health. The containers for study groups 1 and 2 will be open labelled and will be named as "CanDo trial-donor milk" and "CanDo trial-formula". The decision regarding the timing and duration of the supplementation will be determined by the medical team in the well-baby unit based on the specific needs and circumstances of each mother-infant dyad. As this study follows a pragmatic approach, the clinical team will assess the need for supplementation based on the mother-infant dyad's condition. General feeding guidelines, including ad lib/ on-demand parent milk feeding as per the parent's plans, will be in place. The management of hypoglycemia will be according to the recommendations of the Canadian Paediatric Society and in accordance with Mount Sinai's hypoglcemia protocol including routine glucose monitoring for all children born <37 weeks gestation, <10% birth weight for gestation, <2.5 kg or >4.5 kg birth weight, with a supplement provided (dextrose gel followed by supplemental feed) for any glucose <2.6 mmol/L in the first 72 hours after birth (18).

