#### 1.6.4 Practical arrangements for allocating participants to trial groups

Families will be invited to participate in the trial during their antenatal visits to the diabetes and placenta clinics. If they agree to participate, they will be asked to sign the consent form. After giving birth, upon admission to the well-baby unit they will be approached again for confirmation of their willingness to participate in the trial and to add infant's name to the consent form. Infants who are prescribed a supplement will be entered into the trial and randomly assigned to either the donor milk or formula group. Prior to the start of the study, a unique randomization schedule will be generated. The computer-generated randomization schedule will be securely stored in a sealed binder, with each participant's allocation placed in separate envelopes. These envelopes will be securely held in a locked procedure room, either within the well-baby unit. Importantly, to maintain blinding, the study coordinator will access the randomization schedule one envelope at a time during participant enrollment and allocation. This approach ensures that the study coordinator cannot see whether a participant will receive donor milk or formula until the point of assignment. The study allocation will be randomly assigned in a 1:1 ratio, using random blocks of 2 or 4. Furthermore, to prevent potential bias and uphold the integrity of the randomization process, the randomization schedule will incorporate stratification factors. These factors include whether the infant was born to a diabetic mother, whether they are small for gestational age, and the infant's sex. Stratification will facilitate the equitable distribution of supplementation rates across these distinct groups, thereby contributing to the robustness of the randomization process.

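### The glucose outcome is meant to show the effect on hypoglycemia but is fixed at discharge, after low values have been treated, so similar discharge values would not show equal correction

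*Protocol*

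**What the plan says.** Section 1.7 of the protocol, under the heading on length of stay, weight loss and glucose, gives the purpose and the measure in one sentence. The purpose is the effect of donor milk or formula on "improving hypoglycemia in infants, the glucose concentrations at discharge will be extracted from patient charts and compared between groups". The secondary objectives in 1.3.2 give the same time point: "percent weight loss, glucose levels, length of hospital stay at hospital discharge".

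Two other provisions act on glucose before discharge. Section 1.6.3 has "a supplement provided (dextrose gel followed by supplemental feed) for any glucose <2.6 mmol/L in the first 72 hours after birth". Section 1.7 adds an exit rule: if "blood glucose remains <2.6 mmol/L for two consecutive checks, the infant will exit the feeding intervention".

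Section 1.2 shows why glucose matters here: "The reasons for supplemental feeds include hypoglycemia, hyperbilirubinemia, weight loss". Section 1.6.4 sets the moment of randomisation: "Infants who are prescribed a supplement will be entered into the trial and randomly assigned to either the donor milk or formula group". For analysis, 1.9.1 states "Secondary and exploratory outcomes will be assessed using linear and logistic regression models based on the nature of the outcome measure", and the primary analysis "will include all infants as randomized, regardless of feeding protocol compliance". Section 1.9.2 rules out an interim analysis.

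**The concern.** The question asked and the variable measured do not match. Whether a supplement corrects low glucose shows in the values that follow the supplement. A discharge value comes after gel, further feeds and, for infants with persistent lows, departure from the assigned supplement. It partly reflects rescue care, and rescue care works to make the arms alike.

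Hypoglycemia is the first reason for supplementation that the protocol lists, and repeated low glucose is serious enough to take an infant off the intervention. How often glucose stays low on each supplement is therefore a direct short-term safety question. Section 1.15 intends the results to bear on whether access to donor milk in well-baby units should widen. A reassuring comparison of discharge glucose could be quoted as evidence on hypoglycemia when it is not.

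**Working it through.** **Plan's own figure.** The protocol states no sample size, rate or SD for glucose, so there is nothing to reproduce on this outcome. The only number taken from it below is 56 infants per arm (112 in total, section 1.8).

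**Reading the text.**
- Aim (1.7): effect on improving hypoglycemia.
- Measure (1.7 and 1.3.2): glucose at discharge.
- Before discharge (1.6.3): every value <2.6 mmol/L in the first 72 hours is treated.
- Before discharge (1.7): two consecutive values <2.6 mmol/L end the feeding intervention.
- Contrast within 1.7: daily weights are abstracted from the chart; no serial abstraction is stated for glucose.
- Not named as an outcome anywhere: low-glucose episodes, repeat lows, gel use, glucose-triggered exits.

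**How much of a difference survives to discharge (illustration; rates and SD shifts are assumptions).** Let p1 and p0 be the proportions with repeated lows in the two arms, and d the number of SDs by which those infants are still below the others at discharge. Then

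shift in arm mean = (p1 − p0) × d.

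With p1 = 30% and p0 = 10%, tested by a two-sided t-test at 0.05 with 56 per arm (20,000 simulated trials):

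| d | Shift in arm mean | Rejection rate |
|---|---|---|
| 0 | 0.20 × 0 = 0 | 4.8% |
| 0.5 | 0.20 × 0.5 = 0.10 SD | 7.9% |
| 1 | 0.20 × 1 = 0.20 SD | 16.1% |

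The d = 0 row is simply the type I error rate. The closed-form t-test gives 8% power at 0.10 SD and 18% at 0.20 SD; the simulated 16.1% is lower because mixing infants with and without lows adds spread. The difference detectable with 80% power at 56 per arm is 0.53 SD.

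**How precise a direct count would be.** The protocol gives no event rate. The table uses Newcombe 95% intervals for the risk difference, with counts equal to n × assumed rates of 5 v 5%, 10 v 5%, 20 v 10% and 30 v 10%, rounded (for 42 and 28, the first and last pairs only). The denominators 42 and 28 are also assumed, for the case where some infants have too few checks.

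| Evaluable per arm | Counts | Difference (95% CI), points | Half-width |
|---|---|---|---|
| 56 | 3 v 3 | 0.0 (−9.9, 9.9) | 9.9 |
| 56 | 6 v 3 | 5.4 (−5.5, 16.7) | 11.1 |
| 56 | 11 v 6 | 8.9 (−4.7, 22.4) | 13.5 |
| 56 | 17 v 6 | 19.6 (4.6, 33.8) | 14.6 |
| 42 | 2 v 2 | 0.0 (−11.6, 11.6) | 11.6 |
| 42 | 13 v 4 | 21.4 (4.2, 37.6) | 16.7 |
| 28 | 1 v 1 | 0.0 (−14.4, 14.4) | 14.4 |
| 28 | 8 v 3 | 17.9 (−3.3, 37.6) | 20.5 |

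The half-width therefore runs from about 10 to 20 points.

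**The case against.** The best defence is that the wording is loose. The heading in 1.7 refers to the whole initial hospitalization, and 1.3.2 groups glucose with length of stay and weight loss, which are whole-stay measures, so discharge could be read as the time of tallying. Against this, the one sentence that says what is extracted names discharge values, 1.3.2 carries the same time point, and serial abstraction is stated for weight but not for glucose. An analysis plan can choose a model, but it cannot analyse values that were never abstracted. The ambiguity makes the point easier to repair; it does not remove it.

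Second, recovery by discharge is a crude but relevant reading of improvement. That stands, and is a reason to keep discharge glucose as a descriptive measure. It does not show how well each supplement did the correcting.

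Third, a reader might infer that a difference in repeated lows would pass unnoticed. The documents do not support that. To apply the exit rule, staff must detect two consecutive values <2.6 mmol/L, so at least some of these events will be known. What is missing is their status as an outcome counted alike in both arms. It is not even clear that the glucose rule covers both arms, because its paragraph opens by addressing the donor milk group.

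Fourth, the power figures rest on assumed rates and shifts. That is correct. They illustrate a mechanism and do not show that this trial would miss a real difference.

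**Conclusion.** The concern holds in a limited form. The protocol fixes a glucose measure that cannot answer its own question about hypoglycemia: equal discharge values are compatible with different success in correcting low glucose. Under the assumed 30% v 10% rates, at most 0.2 SD would reach the discharge comparison if affected infants leave up to 1 SD lower, well short of the 0.53 SD that 56 per arm can detect with 80% power.

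Two larger conclusions would go too far. The plan does not leave low glucose unmonitored or untreated; clinical management is specified. Nor would a better outcome settle the safety question at this sample size. The matter concerns one secondary outcome and leaves the primary outcome, randomisation and sample size as they are. Severity: minor.

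**What to change.** 1. **Section 1.7:** abstract every in-hospital glucose value with its time, in both arms. Keep discharge glucose as descriptive.
2. **Section 1.3.2:** add a descriptive secondary safety outcome, the proportion of infants with any glucose <2.6 mmol/L after the first study supplement and before discharge. Tabulate persistent low glucose by arm, defined as two consecutive values <2.6 mmol/L of which at least the second follows the first study supplement. A low value that triggered the supplement, followed by another low value, then counts; requiring both after randomisation would miss it. Count identically in both arms and keep values recorded after exit from the intervention.
3. **Section 1.9.1:** analyse as randomised, once, at the end of follow-up. Report the risk difference (donor milk minus formula) with a 95% CI and no formal test. Report the number of post-supplement checks per arm. Any estimate restricted to infants with enough checks is a sensitivity analysis only, because it conditions on something that happens after randomisation and checking frequency may differ by arm in an open-label trial.

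The thresholds and exit rules stay as they are. The cost is a short amendment, extra chart abstraction for 112 infants and one more table, with no new visit, sample or interim look. The interval will be wide. Some infants of diabetic mothers may have few checks, since the monitoring list in 1.6.3 does not name them, although that list is not worded as exhaustive.
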